5.3.2 Dose Delays/Dose Modifications

Dose delays and modifications of cisplatin or carboplatin and etoposide should follow institutional standards (namely, that participants meet re-treatment criteria prior to re-initiation of therapy and may be dose-reduced per institutional standards). However, if dosing of chemotherapy that occurs concurrently with pembrolizumab is held (cohorts A and B), then that day's dosing of pembrolizumab should also be held. If dose –delay of chemotherapy for hematologic or other laboratory toxicity results in a > 4 week delay in therapy, chemotherapy should be discontinued and pembrolizumab may continue as monotherapy. Exceptions to this may be reviewed on a case-by-case basis with sponsor.

Adverse events (both non-serious and serious) associated with pembrolizumab exposure may represent an immunologic etiology. These adverse events may occur shortly after the first dose or several months after the last dose of treatment. Pembrolizumab must be withheld for drug-related

toxicities and severe or life-threatening AEs as per Table 3 below. See Section 5.8.3 for supportive care guidelines, including use of corticosteroids.

Table 3. Toxicity Management and Dose Reduction/Delay/Discontinuation

Toxicity	Hold Treatment For Grade	Timing for Restarting Treatment	Discontinue Subject
Diarrhea/Colitis	2-3	Toxicity resolves to Grade 0-1.	Toxicity does not resolve within 12 weeks of last dose or inability to reduce corticosteroid to 10 mg or less of prednisone or equivalent per day within 12 weeks.
	4	Permanently discontinue	Permanently discontinue
AST, ALT, or Increased Bilirubin	2	Toxicity resolves to Grade 0-1	Toxicity does not resolve within 12 weeks of last dose.
	3-4	Permanently discontinue (see exception below) ¹	Permanently discontinue
Type 1 diabetes mellitus (if new onset) or Hyperglycemia	T1DM or 3-4	Hold pembrolizumab for new onset Type 1 diabetes mellitus or Grade 3-4 hyperglycemia associated with evidence of beta cell failure.	Resume pembrolizumab when patients are clinically and metabolically stable.
Hypophysitis	2-3	Toxicity resolves to Grade 0-1	Toxicity does not resolve within 12 weeks of last dose or inability to reduce corticosteroid to 10 mg or less of prednisone or equivalent per day within 12 weeks.
	4	Permanently discontinue	Permanently discontinue
Hyperthyroidism	3	Toxicity resolves to Grade 0-1	Toxicity does not resolve within 12 weeks of last dose or inability to reduce corticosteroid to 10 mg or less of prednisone or equivalent per day within 12 weeks.
	4	Permanently discontinue	Permanently discontinue
Hypothyroidism	2-4	Therapy with pembrolizumab can be continued while treatment for the thyroid disorder is instituted	Therapy with pembrolizumab can be continued while treatment for the thyroid disorder is instituted.
Infusion Reaction	3-4	Permanently discontinue	Permanently discontinue
Pneumonitis	2	Toxicity resolves to Grade 0-1	Toxicity does not resolve within 12 weeks of last dose or inability to reduce corticosteroid to 10 mg or less of prednisone or equivalent per day within 12 weeks.
	3-4	Permanently discontinue	Permanently discontinue
Renal Failure or Nephritis	2	Toxicity resolves to Grade 0-1	Toxicity does not resolve within 12 weeks of last dose or inability to reduce corticosteroid to 10 mg or less of prednisone or equivalent per day within 12 weeks.
	3-4	Permanently discontinue	Permanently discontinue
All Other Drug-Related Toxicity ²	3 or Severe	Toxicity resolves to Grade 0-1	Toxicity does not resolve within 12 weeks of last dose or inability to reduce corticosteroid to 10 mg or less of prednisone or equivalent per day within 12 weeks.
	4	Permanently discontinue	Permanently discontinue

Note: Permanently discontinue for any severe or Grade 3 drug-related AE that recurs or any life-threatening event. ¹ For patients with liver metastasis who begin treatment with Grade 2 AST or ALT, if AST or ALT increases by greater than or equal to 50% relative to baseline and lasts for at least 1 week then patients should be discontinued. ² Patients with intolerable or persistent Grade 2 drug-related AE may hold study medication at physician discretion. Permanently discontinue study drug for persistent Grade 2 adverse reactions for which treatment with study drug has been held, that do not recover to Grade 0-1 within 12 weeks of the last dose.
			

Dosing interruptions are permitted in the case of medical / surgical events or logistical reasons not related to study therapy (e.g., elective surgery, unrelated medical events, patient vacation, and/or holidays). Subjects should be placed back on study therapy within 4 weeks of the scheduled

interruption, unless otherwise discussed with the Sponsor. The reason for interruption should be documented in the patient's study record.

If dosing interruption or delay occurs, when treatment is restarted, the cycle should restart (exceptions may be discussed with the overall study Sponsor (PI)) and the schedule of assessments going forward should be in accordance with the new start date of that cycle.

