5.5.5.1 Pembrolizumab dose interruption for planned radiation as part of initial treatment

For cohorts A and B, dosing may be interrupted for consolidation thoracic radiation and/or prophylactic cranial irradiation.

Radiation treatments should be confined to a period of 3 weeks (i.e. if both consolidation thoracic radiation and prophylactic cranial irradiation are planned, they should be done concomitantly). Radiation should commence no less than 2 weeks and no more than 4 weeks from the last dose of pembrolizumab. Pembrolizumab should be restarted no less than 2 weeks and no more than 6 weeks after completion of radiation.

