6.6.5 Tumor Imaging and Assessment of Disease

CT scan or MRI (as indicated) will be performed at baseline (within 28 days of initiation of treatment) and after every 2 cycles. Brain MRI should be performed during screening. All scans will be subjected to RECIST 1.1 evaluation and modified RECIST (ir RECIST 1.1)

Participants in cohorts A and B should have brain MRI performed during standard planned radiologic assessment at the completion of chemotherapy.

Participants in cohort C and participants in cohort A and B who do not have brain metastases after completion of chemotherapy and DO NOT undergo prophylactic cranial irradiation should have brain MRI performed every 12 weeks during planned radiologic assessments (after completion of chemotherapy).

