6.6.9.4 Post-treatment visits—Follow up Visits

Subjects who discontinue trial treatment for a reason other than disease progression will move into the Follow-Up Phase and should be assessed every 6 weeks (42 ± 7 days) by radiologic imaging to monitor disease status. After 27 months (the maximum time of treatment + 3 months), the imaging time point will occur every 12 weeks (± 7 days). Every effort should be made to collect information regarding disease status until the start of new anti-neoplastic therapy, disease progression, death, end of the study or if the subject begins retreatment with pembrolizumab as detailed in Section 6.6.9.5 Information regarding post-study anti-neoplastic treatment will be collected if new treatment is initiated.

Subjects who are eligible to receive retreatment with pembrolizumab according to the criteria in Section 6.6.9.6 will move from the follow-up phase to the Second Course Phase when they experience disease progression. Participants treated in the second course phase should follow the schedule of assessments as for maintenance pembrolizumab cycles in section 7.0.

CONFIDENTIAL

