Vital signs	X	X	X	X	X	X		X ^g		X
Height	X	X	X	X	X	X				X
Weight	X	X		X	X	X				X
Performance status	X	X		X	X	X		X ^g		X
CBC w/diff, plts ^d	X	X	X	X	X	X		X ^g		X
Serum chemistry ^e	X	X	X	X	X	X		X ^g		X
EKG	X									
Adverse event evaluation	X	X	X	X	X	X	X	X ^g	X ⁱ	X
Tumor measurements/radiologic evaluation ^f	X			X	X	X		X ^g		X
Pulmonary Function Tests	X									
B-HCG	X ^e									X ^e
Tumor (archival) biopsy ⁱ	X									
Tumor biopsy (pre-treatment) ^j	X									
Tumor biopsy (post-treatment), optional						X ^h				
Blood samples for correlative studies		X ^k	X ^k		X ^k	X ^k				X ^k

^aPembrolizumab will be given on day 1 of each cycle. Carboplatin or cisplatin will be given on day 1 of each cycle. Etoposide will be given on days 1, 2, and 3 of each cycle.

^bCohort A participants will be treated with combination chemotherapy + pembrolizumab for a minimum of 4 and a maximum of 6 cycles. Cohort B participants will be treated for a minimum of 3 and a maximum of 5 cycles of combination therapy if they had only one cycle prior to study and a minimum of 2 or maximum of 4 if they had 2 cycles of therapy prior to study.

^cContinued maintenance pembrolizumab will be given on day 1 of each cycle after completion of chemotherapy with 1st dose 3 weeks after last cycle day 1 up through a maximum of 17 cycles following completion of chemotherapy. Interruption of therapy for planned radiation may occur as detailed in sections 5.5.5.1 and 5.11.1

^dSee Table 5 for details.

^eSee Table 5. BHCG, Free T4, T3, PT/PTT, uric acid will be drawn at screening only and thereafter as clinically indicated.

^fRadiologic assessment should include chest/abdomen/pelvis CT scan at baseline following by CT scan or MRI as appropriate to follow known areas of disease. Participants who have untreated brain metastases should have brain MRI at every scheduled radiologic assessment. For participants who DO NOT have baseline brain metastases, brain MRI should be performed on the planned radiologic assessment after completion of chemotherapy. For participants who do not have brain metastases after completion of chemotherapy and DO NOT undergo prophylactic cranial irradiation, brain MRI should be performed every 12 weeks following the completion of chemotherapy. Other radiologic assessments should occur every 6 weeks (within 7 days prior to every other cycle—prior to cycle 3, 5, 7, 9, etc).

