8.1 Antitumor Effect—Solid Tumors

For the purposes of this study, participants should be re-evaluated for response every 6 weeks during therapy (and for 1st 18 weeks after therapy completion) followed by re-evaluation every 12 weeks. In addition to a baseline scan, confirmatory scans should also be obtained no less than 4 weeks following initial documentation of objective response (preferably at 6 weeks or next planned assessment).

Response and progression will be evaluated in this study using the new international criteria proposed by the Response Evaluation Criteria in Solid Tumors (RECIST) guideline (version 1.1) [*Eur J Ca* 45:228-247, 2009]. Changes in the largest diameter (unidimensional measurement) of the tumor lesions and the shortest diameter in the case of malignant lymph nodes are used in the RECIST criteria.

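### Tumour imaging runs on two clocks, six weeks and two cycles, and the restart rule does not exempt scans, so dosing breaks can delay detected progression near the PFS benchmark

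*Combined protocol and SAP*

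**What the plan says.** The imaging interval is stated in several places.

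- Section 8.1, by calendar: "participants should be re-evaluated for response every 6 weeks during therapy".
- Section 6.6.5, by cycle: a baseline scan "and after every 2 cycles".
- Section 7, calendar for cohorts A and B, footnote f, both at once: "Other radiologic assessments should occur every 6 weeks (within 7 days prior to every other cycle". Footnote d for cohorts C and D says the same.
- Section 5.3.2: when treatment restarts after an interruption or delay, the cycle restarts and "the schedule of assessments going forward should be in accordance with the new start date of that cycle". Exceptions to restarting the cycle may be discussed with the sponsor. Imaging is not mentioned.
- Section 6.6.9.4, by calendar, but only for patients who have stopped treatment without progression: they "should be assessed every 6 weeks (42 ± 7 days) by radiologic imaging to monitor disease status".

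Two kinds of interruption matter. Table 3 in section 5.3.2 allows toxicity holds up to 12 weeks from the last dose. Section 5.5.5.1 allows a break for radiation in cohorts A and B. Radiation starts 2 to 4 weeks after the last dose and is confined to 3 weeks, and then "Pembrolizumab should be restarted no less than 2 weeks and no more than 6 weeks after completion of radiation".

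Median PFS is a secondary endpoint set against a historical 5.4 months (section 3.3), with PFS also read at 3 and 6 months (section 2.2). Section 8.1.6 censors at the last disease evaluation and has no rule for late or missed scans.

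**The concern.** Six weeks and two cycles are the same interval only while dosing is on time. Once a dose is held, the only text that says what happens to assessments ties them to the restarted cycle. Two sites could both follow the protocol and scan on different clocks.

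Progression that occurs in a stretched interval is dated at the next scan. The radiation break follows chemotherapy. With 4 to 6 three-weekly cycles the last combined dose is at weeks 9 to 15, and a restart 7 to 13 weeks later falls at weeks 16 to 28. That window contains the 5.4-month benchmark (23.5 weeks) and the 6-month landmark (26.1 weeks). A scan not taken during the gap cannot be recovered at analysis.

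**Working it through.** **Plan figures.** The documents give no PFS power, event count or test to reproduce. The only design calculation, 88% power for the paired PD-L1 comparison, reproduces at 88.3% (noncentral t, n = 12, effect size 1.0, two-sided 0.05) and is not affected here.

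**Assumptions not in the documents.** Exponential PFS with true median 5.4 months, counted from the first dose; progression found only at the next scan, apart from a share of events found off-scan (0% or 30%, by death or clinically); break after on-study cycle 4, 5 or 6; dose gap uniform on 7 to 13 weeks; 25% to 100% of patients taking the break. Cycles 4 to 6 are cohort A's pattern. Cohort B has 3 to 5 on-study cycles; moving the break one cycle earlier stays inside the range below.

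**1. Length of the break.** Shortest: 2 + 3 + 2 = 7 weeks between doses. Longest: 4 + 3 + 6 = 13 weeks. A 7-week gap misses the doses due at weeks 3 and 6, which matches the two missed doses stated in the synopsis. A 13-week gap misses four (weeks 3, 6, 9, 12). Three weeks is a maximum for radiation. If the 10 fractions of section 5.5.7 take 2 weeks (assumed five per week), the minimum is 2 + 2 + 2 = 6 weeks.

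**2. Scan gaps on the cycle-linked reading.** With six cycles the sixth dose is at week 15. Scans fall at weeks 6, 12 and 18 (after cycle 6, per section 6.6.5). With a 13-week gap, cycle 7 starts at week 28. The next scan is at week 28, or at week 34 if the week-18 scan is counted as the pre-cycle-7 scan. The gap is 10 or 16 weeks. Most other patterns also give 10–16 weeks; five cycles with a scan at completion of chemotherapy gives 7–13. A 12-week toxicity hold plus the other 3-week cycle of the pair gives 15.

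**3. Single patterns.** S(t) = 2^(−t/23.5), and 6-month PFS is read at the last scan before week 26.1.

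| Six cycles | Last scan | 6-month PFS |
|---|---|---|
| Calendar scans | week 24 | 49% |
| 13-week gap | week 18 | 59% |
| 7-week gap, scan before cycle 7 | week 22 | 52% |
| 9-week gap, scan before cycle 7 | week 24 | 49% |
| 10-week gap, scan before cycle 7 | week 25 | 48% |

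The observed median is the first scan with S ≤ 0.5: week 24 (5.5 months) on the calendar, and week 28 (6.4 months) with the 13-week gap and a scan before cycle 7. If the true median were 4.7 months, a 7-week gap would lower the observed median from 5.52 to 5.06 months.

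Shorter courses with the longest gap can read higher. Five cycles with a completion scan at week 15 gives 2^(−15/23.5) = 64%. Four cycles with no scan between weeks 12 and 28 gives 2^(−12/23.5) = 70%; that requires overlooking the scan that footnote f places before cycle 5.

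**4. Averages (simulation).**

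| Patients taking the break | Observed median, months | Change in 6-month PFS |
|---|---|---|
| none (calendar scans) | 5.5 | reference, 48–49% |
| 25% | 5.8–6.3 | +1 to +2 points |
| 50% | 6.0–6.6 | +2 to +4 points |
| 100% | 6.1–6.7 | +3 to +7 points |

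**5. Scale.** The 95% CI for a 5.4-month median with all events observed is 5.4 × exp(±1.96/√n): 3.3–9.0 months for n = 15 and 4.2–7.0 for n = 60.

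**The case against.** The strongest reply is that this is a wording conflict, not a design that sets late scans. Six weeks appears in section 8.1 and in both calendar footnotes. The restart rule governs assessments once treatment resumes, does not suspend imaging during a hold, and lets exceptions to the cycle restart be discussed with the sponsor. That is fair as far as it goes. But no text keeps scans on the calendar during a hold, and the calendar rule in section 6.6.9.4 covers only patients who have stopped treatment.

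Other limits stand. The radiation break is optional and no uptake figure is given. Deaths count as PFS events and are not delayed. The primary PD-L1 endpoint is untouched, and the shift is small beside the sampling error, although a systematic shift does not shrink with more patients.

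A reader might infer three stronger claims that the documents do not support.

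- That 6-month PFS in a six-cycle course would read 70%. This needs no scan between weeks 12 and 28, but section 6.6.5 calls for one after cycle 6. Reaching 64–70% with shorter courses requires every patient to take the longest break.
- That PFS is inflated against the historical control. The control's scan schedule is not given; if it was as sparse, the net bias could be nil or reversed.
- That cohorts C and D are free of planned breaks. Footnote a of their calendar allows interruption for planned or palliative radiation and cites section 5.5.5.1, which names only cohorts A and B.

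**Conclusion.** The point holds as an unresolved conflict between two imaging clocks, with a restart rule that lets the cycle clock prevail after a delay. Under the stated assumptions, cycle-linked scanning in cohorts A and B raises 6-month PFS by about 1 to 7 points on average and gives an observed median of about 5.8–6.7 months, against 5.5 with calendar scans. A six-cycle course with the longest break reads 59% against 49%. The average shift is upward, but particular break lengths give none or a small fall. The size depends on uptake and length of the break, neither of which the documents supply. The consequence is limited to a secondary, descriptive comparison. It is still worth correcting before data accrue, because a missing scan cannot be replaced later.

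**What to change.** - State once that tumour imaging is every 6 weeks (±7 days) by calendar from the first on-study dose, regardless of dose delays, cycle restarts or radiation breaks.
- Exempt imaging from the restart rule in section 5.3.2.
- Align section 6.6.5 and calendar footnotes f (cohorts A and B) and d (cohorts C and D) with section 8.1, removing the cycle count as the trigger.
- Optionally, add an interval-censored PFS sensitivity analysis for late or missed scans.
- Reconcile the synopsis (two missed doses), section 5.5.5.1 (up to 13 weeks between doses, cohorts A and B) and footnote a for cohorts C and D on the length and cohort scope of the radiation break. Which dosing rule applies is for the investigators to settle.

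The cost is a short amendment. It requires no more scans than section 8.1 already asks for and changes no dosing rule. The small downside is that scan and dosing visits may fall on different days.

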5.4 Pre-Treatment Criteria

5.4.1 Cycle 1, Day 1

Participants should meet treatment criteria for platinum and etoposide per institutional standards. For participants entering cohorts C or D, prior treatment-related toxicities should have resolved to grade 1 or baseline (with the exception of anemia (Grade 2 allowed), alopecia, and neuropathy (grade 2 allowed)).

5.4.2 Subsequent Cycles

Participants should meet treatment criteria for platinum and etoposide per institutional standards.

5.5 Agent Administration

5.5.1 Pembrolizumab

Pembrolizumab 200 mg will be administered as a 30 minute IV infusion on day 1 of every 21 day cycle.

After completion of chemotherapy, pembrolizumab will be administered as monotherapy for up to a total of 34 cycles (2 years of monotherapy).

Sites should make every effort to target infusion timing to be as close to 30 minutes as possible. However, given the variability of infusion pumps from site to site, a window of -5 minutes and +10 minutes is permitted (i.e., infusion time is 30 minutes: -5 min/+10 min).

The Pharmacy Manual for pembrolizumab contains specific instructions for the preparation of the pembrolizumab infusion fluid and administration of infusion solution.

5.5.2 Cisplatin or carboplatin and etoposide.

Cisplatin, carboplatin, and etoposide should be administered as per institutional standards.

Cisplatin 75 mg/m² will be administered as an IV infusion per institutional standards on day 1 of every 21 day cycle for up to 6 cycles for cohort A and for up to 5 cycles for cohort B (total number of cycles of chemotherapy on and off study should not total more than 6)

Carboplatin AUC 6 will be administered as an IV infusion per institutional standards on day 1 of every 21 day cycle for up to 6 cycles for cohort A and for up to 5 cycles for cohort B (total number of cycles of chemotherapy on and off study should not total more than 6)

Etoposide 100 mg/m² will be administered as an IV infusion per institutional standards on day 1, day 2, and day 3 of every 21 day cycle for up to 6 cycles for cohort A and for up to 5 cycles for cohort B (total number of cycles of chemotherapy on and off study should not total more than 6).

5.5.3 Availability

Pembrolizumab is provided by Merck and study drug to each site will be supplied directly by Merck.

5.5.4 Preparation

Following reconstitution with sterile water for injection, Pembrolizumab (MK-3475) infusion solutions should be prepared in **0.9% Sodium Chloride Injection, USP** (normal saline) or regional equivalent and the final concentration of pembrolizumab (MK-3475) in the infusion solutions should be between 1 mg/mL and 10 mg/mL.

If normal saline is not available, 5% Dextrose Injection, USP or regional equivalent (5% dextrose) is permissible. Please note, the preferred diluent is 0.9% Sodium Chloride and 5% dextrose is only permissible if normal saline is not available.

Pembrolizumab (MK-3475) SHOULD **NOT** BE MIXED WITH OTHER DILUENTS unless instructed by NYULMC PCC in writing. Refer to pharmacy manual for further details.

5.5.5 Timing of Administration

Pembrolizumab will be administered at least 30 minutes prior to premedication for the chemotherapies.

Trial treatment should be administered on Day 1 (or days 1, 2, and 3 for etoposide) of each cycle after all procedures/assessments have been completed.

All trial treatments will be administered on an out-patient basis.

For subjects who experience disease progression, investigators may elect to interrupt treatment by deferring the decision to continue/discontinue treatment in the trial until confirmation of disease progression per RECIST 1.1 at least 28 days from the date of imaging demonstrating disease progression. Subjects for whom disease progression is not confirmed on subsequent imaging may resume treatment.

5.5.5.1 Pembrolizumab dose interruption for planned radiation as part of initial treatment

For cohorts A and B, dosing may be interrupted for consolidation thoracic radiation and/or prophylactic cranial irradiation.

Radiation treatments should be confined to a period of 3 weeks (i.e. if both consolidation thoracic radiation and prophylactic cranial irradiation are planned, they should be done concomitantly). Radiation should commence no less than 2 weeks and no more than 4 weeks from the last dose of pembrolizumab. Pembrolizumab should be restarted no less than 2 weeks and no more than 6 weeks after completion of radiation.

